10.5.2.2. Handling of Partial Dates

Element	Reporting Detail
Concomitant Medications	 Partial dates for any concomitant medications recorded in the CRF will be imputed using the following convention: If the partial date is a start date, a '01' will be used for the day and 'Jan' will be used for the month If the partial date is a stop date, a '28/29/30/31' will be used for the day (dependent on the month and year) and 'Dec' will be used for the month. The recorded partial date will be displayed in listings.
Adverse Events	 Any partial dates for adverse events will be raised to data management. If the full date cannot be ascertained, the following assumptions will be made: If the partial date is a start date, a '01' will be used for the day and 'Jan' will be used for the month. However, if these results in a date prior to Week 1 Day 1 and the event could possibly have occurred during treatment from the partial information, then the Week 1 Day 1 date will be assumed to be the start date. The AE will then be considered to start on-treatment (worst case). If the partial date is a stop date, a '28/29/30/31' will be used for the day (dependent on the month and year) and 'Dec' will be used for the month.

10.6. Appendix 6: Values of Potential Clinical Importance

10.6.1. Laboratory Values

Haematology				
Laboratory Parameter	Units	Category	Clinical Concern Range	
			Low Flag (< x)	High Flag (>x)
		Male		0.54
Hematocrit	Ratio of 1	Female		0.54
		Δ from BL	↓0.075	
	e.//	Male		180
Hemoglobin	g/L	Female		180
		Δ from BL	↓25	
Lymphocytes	x10 ⁹ / L		0.8	
Neutrophil Count	x10 ⁹ / L		1.5	
Platelet Count	x10 ⁹ / L		100	550
While Blood Cell Count (WBC)	x10 ⁹ / L		3	20

Clinical Chemistry				
Laboratory Parameter	Units	Category	Clinical Concern Range	
			Low Flag (< x)	High Flag (>x)
Albumin	mmol/L		30	
Calcium	mmol/L		2	2.75
Creatinine	mmol/L	Δ from BL		↑ 44.2
Glucose	mmol/L		3	9
Magnesium	mmol/L		0.5	1.23
Phosphorus	mmol/L		0.8	1.6
Potassium	mmol/L		3	5.5
Sodium	mmol/L		130	150
Total CO2	mmol/L		18	32

Liver Function			
Test Analyte	Units	Category	Clinical Concern Range
ALT/SGPT	U/L	High	\geq 2x ULN
AST/SGOT	U/L	High	\geq 2x ULN
AlkPhos	U/L	High	\geq 2x ULN
T Bilirubin	µmol/L	High	≥ 1.5xULN
	µmol/L		1.5xULN T. Bilirubin
T. Bilirubin + ALT		High	+
	U/L		\geq 2x ULN ALT

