2. INTRODUCTION

2.1. Brief background

Albumin is the most prevalent protein in human plasma (35-54 g/L) and has a half-life in humans of approximately 19 days [Peters, 1985] [Peters, 1996(a)]. Total extravascular albumin is about twice that of the intravascular pool, and exchange occurs between these pools at a rate of 4-5% total albumin/hour [Peters, 1996(b)]. However, this is a simplification of a complex process. Certain organs (e.g. lungs, liver, kidney) show rapid exchange with intravascular albumin, and others (e.g. skin, muscle), that account for a large amount of extravascular albumin due to their size, show a much slower exchange [Peters, 1996(b)].

GSK3128349 is a human domain antibody (dAb) that binds non-covalently to serum albumin with high affinity (also referred to as an 'AlbudAb'). It contains a cysteine residue engineered at the C terminus of the molecule that can be used for the covalent attachment of a pharmacologically active entity (Figure 1). As such, GSK3128349 is a scaffold that has of itself no pharmacological action, but has the potential to be conjugated with a pharmacologically active entity [O'Connor-Semmes, 2014]. [The Cterminal cysteine of GSK3128349 used in the current study is blocked with N-ethylmaleimide in order to avoid undesirable chemical reactivity towards serum proteins or covalent dimerization.]

Figure 1 Schematic of GSK3128349 AlbudAb, depicted binding to albumin (HSA) and with a conjugated therapeutic drug.

Typically, dAbs are small (~15 kDa) and therefore are excreted renally in a matter of hours. Due to the combination of the high affinity of GSK3128349 for albumin and the high concentrations of albumin, it is expected that GSK3128349 will be bound to albumin the majority of the time. Therefore, AlbudAbs, like GSK3128349, form a complex too big to be subject to renal clearance. Furthermore, the binding of

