4.4. Risk Assessment and Management

Summaries of findings from non-clinical studies conducted with GSK3128349 can be found in the GlaxoSmithKline Document Number 2014N199359_00 Investigator Brochure. Although GSK3128349 was well tolerated in a rat toxicology study, it has not been tested in humans before therefore potential adverse affects may be encountered. The table below summarises the potential key risks and mitigation strategy for this protocol.

Table 3Summary of protocol-specific risks and mitigation strategies

Potential risk	Summary of data	Impact- eligibility criteria	Strategy-monitoring/stopping criteria			
Renal injury	The AlbudAb platform has been associated with degenerative changes in the proximal renal tubule in the mouse with repeat and long duration (greater than 4 weeks) dose regimen only. These observations appear reversible on washout and have not been observed in monkey safety studies (see summary Section 4.3 and IB for detailed information).	Subjects with history of renal disease and/or abnormalities are excluded, including proteinuria and reduced estimated Glomerular Filtration Rate (eGFR) (see exclusion criteria Section 5.2 points 3, 11 and 12 for more information).	Renal function and proteinuria will be closely monitored using standard serum and urine chemistry biomarkers.			
Acute infusion reaction	Infusion / acute allergic reactions upon administration are a potential risk with all protein therapeutics.	Subjects are excluded with a history of sensitivity to any of the study treatment, or components thereof or a history of drug or other allergies.	Subjects will be monitored for symptoms of hypersensitivity or other potentially immune- mediated reactions post-infusion, and will be treated promptly as appropriate.			
Immunogenicity	As is the case for all protein therapeutics, antibodies may develop against the agent administered.	None	Immunogenicity samples will be drawn at baseline and following dosing of GSK3128349 to monitor the immunogenicity potential of this molecule.			
Radioactivity exposure	The total radioactivity exposure due to combined PET ligand	Subjects with previous involvement in a research	After completion of the first 2 subjects, dosimetry analysis will			

2014N202021_00

CONFIDENTIAL

Potential risk	Summary of data	Impact- eligibility criteria	Strategy-monitoring/stopping criteria

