7.3.6. Clinical Safety Laboratory Assessments

Values for the laboratory parameters should be within the normal range for the relevant subject population as specified by the clinical laboratory, which will be an accredited facility. Subjects with screening laboratory values outside of the normal range will be accepted into the study only after the Investigator, or a qualified designee, and the GSK

Medical Monitor have determined that the out of range value(s) are not clinically significant and would not pose an increased risk to the subject.

At the Principal Investigator and GSK Medical Monitor's discretion, additional laboratory tests other than those outlined below may be included to further assess safety and tolerability.

Hematology, clinical chemistry, urinalysis and additional parameters to be tested are listed below:

Hematology

	8/			
Platelet Count	RBC Indices :	Automated WBC Differential:		
RBC Count	MCV	Neutrophils		
WBC Count (absolute)	МСН	Lymphocytes		
Reticulocyte Count	MCHC	Monocytes		
Hemoglobin		Eosinophils		
Hematocrit Basophils		Basophils		
RBC- Red blood cell; WBC- White Blood Cell; MCV- Mean Corpuscular Volume; MCH- Mean				
Corpuscular Hemoglobin; MCHC- Mean Corpuscular Hemoglobin Concentration.				

Clinical Chemistry

BUN	Potassium	AST (SGOT)	Total and direct bilirubin
Creatinine	Chloride	ALT (SGPT)	Uric Acid
(eGFR)			
Glucose	Calcium	GGT	Albumin
Sodium		Alkaline phosphatase	Total Protein
BUN- Blood Urea Nitrogen; AST (SGOT)- Aspartate Aminotransferase (Serum Glutamic Oxaloacetate			
Transaminase); eGFR-ALT- Alanine Aminotransferase (SGPT)- (Serum Glutamic Pyruvic Transaminase);			

GGT- Gamma Glutamyl Transpeptidase.

Routine Urinalysis

Specific gravity
pH, glucose, protein, blood and ketones by dipstick
Microscopic examination (if blood or protein is abnormal) includes RBC, WBC, casts
and bacteria

Other tests

HIV		
Hepatitis B (HBsAg)		
Hepatitis C (Hep C antibody if second generation Hepatitis C antibody positive, a		
hepatitis C antibody Chiron RIBA immunoblot assay (or other third generation		
immunoassay) should be reflexively performed on the same sample to confirm the		
result)		
Alcohol and drug screen (to include at minimum: amphetamines, barbiturates, cocaine,		
opiates, cannabinoids and benzodiazepines).		
Proteinuria (UPCR)		
NOTE :		
Details of Liver Safety Required Actions and Follow-Up Assessments after a		
liver event are given in Appendix 2.		

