8.2.2. Overview of Planned Clinical Laboratory Analyses

The safety analyses will be based on the Safety population, unless otherwise specified.

Table 8 provides an overview of the planned analyses, with further details of data displays being presented in Appendix 8: List of Data Displays.

Table 8 Overview of Planned Clinical Laboratory Analyses

Endpoint / Parameter/ Display Type		Abs	olute	Change from BL			
	Sum	mary	Individual	Sumr	nary	ary Individual	
	Т	F	L	Т	F	L	
Chemistry							
Clinical Chemistry Parameters	Y			Y			
Chemistry Data for Subjects with Abnormalities of Potential Clinical Concern			Y				
Chemistry Data Abnormalities of Potential Clinical Importance			Y				
Hematology							
Hematology Parameters	Y			Y			
Hematology Data for Subjects with Abnormalities of Potential Clinical Concern			Y				
Hematology Data Abnormalities of Potential Clinical Importance			Y				
Urinalysis							
Urine Concentration Data	Y		Y	Y			

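### SAP 10.6.1 gives the albumin flag in mmol/L, which the protocol's own albumin range rules out; the creatinine flag has the same unit and should be checked

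*SAP*

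**What the plan says.** SAP 10.6.1 tabulates nine clinical chemistry limits of potential clinical importance, and the unit column reads mmol/L in all nine rows. The albumin row, a low flag, reads "Albumin mmol/L 30". The creatinine row, a flag on change from baseline, reads "Creatinine mmol/L Δ from BL ↑ 44.2". The liver function table in the same section does use a micromolar unit: "T Bilirubin µmol/L High".

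Protocol 2.1 gives albumin in mass units: "Albumin is the most prevalent protein in human plasma (35-54 g/L". The same section gives the size of a domain antibody: "Typically, dAbs are small (~15 kDa". Protocol 7.3.6 includes albumin and creatinine in the chemistry panel (one row of it reads "Glucose Calcium GGT Albumin") but states no units.

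SAP Table 8 (section 8.2.2) provides individual chemistry data through two displays only. The first is "Chemistry Data for Subjects with Abnormalities of Potential Clinical Concern"; the second shows the abnormal values themselves. They correspond to Listings 15 and 16 in SAP 10.8.10. Neither 10.8.10 nor 10.8.11 contains a listing of all chemistry data, and nothing elsewhere in the SAP restates or corrects the two units.

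**The concern.** A low flag should lie at or below the bottom of the normal range. In g/L, 30 does so; in mmol/L it cannot be reconciled with 35-54 g/L. A unit repeated down the whole column suggests that it was copied without checking each analyte.

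Because these limits decide who and what appears in Listings 15 and 16, a wrong unit can make the listings either indiscriminate (everyone flagged on albumin) or blind (no creatinine rise flagged). Creatinine matters because it is the only serum marker of renal function given a limit in 10.6.1; BUN is in the protocol panel but has none. Renal injury is the first risk in protocol Table 3, where the stated mitigation is: "Renal function and proteinuria will be closely monitored using standard serum and urine chemistry biomarkers".

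**Working it through.** The SAP does not derive its limits, so there is no plan calculation to reproduce. The check is whether each number is possible in its printed unit.

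**Inputs**
- Albumin limit 30 mmol/L and creatinine limit 44.2 mmol/L (rise): SAP 10.6.1.
- Plasma albumin 35-54 g/L and domain antibody about 15 kDa: protocol 2.1.
- Molar mass of albumin: not in the documents. I use 15 kDa as a deliberately low floor and 60-70 kDa as an assumption.
- Baseline creatinine: not in the documents. I assume 0.08-0.12 mmol/L.

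**Albumin.** Concentration in mmol/L = (g/L) / (molar mass in kDa).

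| Molar mass | 35-54 g/L in mmol/L | 30 mmol/L as a multiple |
|---|---|---|
| 15 kDa | 35/15 = 2.3 to 54/15 = 3.6 | 30/3.6 = 8.3 to 30/2.33 = 12.9 |
| 60-70 kDa (assumed) | 35/70 = 0.50 to 54/60 = 0.90 | 30/0.90 = 33 to 30/0.50 = 60 |

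In reverse, for even the top of the range to reach 30 mmol/L, albumin would have to weigh 54/30 = 1.8 kDa; for the bottom, 35/30 = 1.2 kDa. The first is about 8 times less than a molecule the protocol calls small (15/1.8 = 8.3). Protocol 2.1 also says that the domain antibody bound to albumin is too large for renal clearance, which does not fit an albumin of 1 to 2 kDa. Read in g/L, the flag lies 5 g/L below the range (5/35 = 14%), which is workable.

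**Creatinine (on the assumed baseline).**
- As printed: 44.2/0.12 = 368 and 44.2/0.08 = 553 times baseline, a rise that will not occur.
- Read as µmol/L: 0.0442/0.12 = 37% and 0.0442/0.08 = 55% of baseline, a usable flag.

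**How much of the table is affected.** Of the nine rows, magnesium, phosphorus and total CO2 are not in the protocol 7.3.6 panel. That leaves 9 - 3 = 6 measured limits: albumin, calcium, creatinine, glucose, potassium and sodium. One of the six is certainly mislabelled, two if creatinine is confirmed; the other four do not raise this problem.

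**Effect on the listings.** The documents do not give the laboratory's units, so the result depends on the programming.
1. Results converted to the printed unit: every albumin value is flagged and no creatinine rise is. Chemistry is taken post-dose at 24 h and on Days 6, 13, 20 and 31 (protocol 7.1.2) and on Day 43 (7.1.3), six times. That gives 6 x 6 = 36 to 6 x 8 = 48 post-dose albumin flags in six to eight subjects. If the screening and Day -1 samples are also flagged, it is 8 x 6 = 48 to 8 x 8 = 64. Listing 15 then contains every subject. Listing 16 fills with uninformative albumin rows and has no creatinine rows, but still selects correctly on the other analytes.
2. Bare numbers applied to results in g/L and µmol/L: both flags work.
3. A program that requires the units to match, with results in g/L and µmol/L: neither flag fires. A subject whose only abnormality is a creatinine rise appears in neither listing.

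**The case against.** The strongest reply accepts the albumin misprint but says that little follows from it. First, the creatinine half has no anchor in the documents: the baseline is assumed, and mmol/L differs from µmol/L by a single character. The SAP text as read from the PDF has a garbled entry in the haemoglobin unit cell of the same appendix, so a lost µ is possible. Second, the renal argument belongs to creatinine, not to the proven albumin error. Third, harm depends on the programming. In case 2 nothing goes wrong. In case 1 Listing 15 prints the full chemistry of everyone, so creatinine values remain visible. Only case 3 could hide a rise, and no section describes such a program. Fourth, safety handling does not use these limits: protocol 7.3.6 relies on the laboratory's own ranges and on repeat testing of clinically significant abnormalities, protocol 5.4.3 bases renal referral on haematuria, UPCR and eGFR, and Tables 4.3 and 4.4 summarise all chemistry values and changes.

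Most of this stands as a limit on size. Creatinine is a query, although the intact µ in the bilirubin rows and the unbroken mmol/L column make a copied unit plausible. None of it rescues the albumin cell: no single lost character turns g/L into mmol/L, and g/L survives in the haemoglobin row. Avoiding the fault by programming the bare number means departing from the SAP as written.

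**Conclusion.** The concern holds and is minor. The albumin unit in SAP 10.6.1 is wrong as written. This follows from the protocol's own 35-54 g/L at any molar mass from 15 kDa upwards, so confidence is high. For creatinine, confidence is medium: the conclusion rests on an assumed baseline of 0.08-0.12 mmol/L, and the cell needs checking against the source PDF.

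One of six measured chemistry limits is certainly affected, two if creatinine is confirmed. The consequence is confined to the content of Listings 15 and 16, and whether it appears depends on how the limits are programmed. The PET endpoints, Tables 4.3 and 4.4, adverse event reporting and the renal referral rule in protocol 5.4.3 are unaffected.

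**What to change.** Correct the albumin unit in SAP 10.6.1. Check the creatinine cell in the original PDF and correct it if it reads mmol/L there too. The printed numbers are consistent with g/L for albumin and µmol/L for creatinine. Confirm both against the laboratory's reporting units before Listings 15 and 16 are programmed. The cost is one or two cells in one table, with no new data, analyses or displays.

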10.6.2. ECG

ECG Parameter	Units	Clinical Concern Range		
		Lower	Upper	
Absolute				
	msec	> 450		
Abaaluta OTa Intonval		> 450	≤ 479	
Absolute QTC Interval		≥ 480	≤ 499	
		≥ 500		
Absolute PR Interval	msec	< 110	> 220	
Absolute QRS Interval	msec	< 75	> 110	

10.6.3. Vital Signs

Vital Sign Parameter	Units	Clinical Concern Range		
(Absolute)		Lower	Upper	
Systolic Blood Pressure	mmHg	< 85	> 160	
Diastolic Blood Pressure	mmHg	< 45	> 100	
Heart Rate	bpm	< 40	> 110	

10.7. Appendix 7 – Abbreviations & Trade Marks

10.7.1. Abbreviations

Abbreviation	Description	
AE	Adverse Event	
AIC	Akaike's Information Criteria	
A&R	Analysis and Reporting	
CDISC	Clinical Data Interchange Standards Consortium	
CI	Confidence Interval	
CPMS	Clinical Pharmacology Modelling & Simulation	
CS	Clinical Statistics	
CSR	Clinical Study Report	
CTR	Clinical Trial Register	
CV _b /CV _w	Coefficient of Variation (Between) / Coefficient of Variation (Within)	
DOB	Date of Birth	
DP	Decimal Places	
eCRF	Electronic Case Record Form	
IA	Interim Analysis	
ICH	International Conference on Harmonisation	
IDMC	Independent Data Monitoring Committee	
IDSL	Integrated Data Standards Library	
IMMS	International Modules Management System	
IP	Investigational Product	
ITT	Intent-To-Treat	
GUI	Guidance	
LOC	Last Observation Carries Forward	
MMRM	Mixed Model Repeated Measures	
PCI	Potential Clinical Importance	
PD	Pharmacodynamic	
PDMP	Protocol Deviation Management Plan	
РК	Pharmacokinetic	
PP	Per Protocol	
QC	Quality Control	
QTcF	Frederica's QT Interval Corrected for Heart Rate	
QTcB	Bazett's QT Interval Corrected for Heart Rate	
RAP	Reporting & Analysis Plan	
SAC	Statistical Analysis Complete	
SDTM	Study Data Tabulation Model	
SOP	Standard Operation Procedure	
ТА	Therapeutic Area	
TFL	Tables, Figures & Listings	
GSK	GlaxoSmithKline	

10.7.2. Trademarks

Trademarks of the GlaxoSmithKline		
Group of Companies		

HARP

Trademarks not owned by the GlaxoSmithKline Group of Companies

SAS

WinNonlin

10.8. Appendix 8: List of Data Displays

10.8.1. Data Display Numbering

The following numbering will be applied for RAP generated displays

Section	Tables	Figures
Study Population	1.1 to 1.8	
PET	2.1 to 2.8	2.1 to 2.7
Pharmacokinetic	3.1 to 3.7	3.1 to 3.9
Safety	4.1 to 4.13	
Section	Listi	ings
ICH Listings	1 tc	23
Other Listings	24 te	o 38

10.8.2. Mock Example Shell Referencing

Non IDSL specifications will be referenced as indicated and if required an example mock-up displays provided in Appendix 9: Example Mock Shells for Data Displays.

Section	Figure	Table	Listing
Study Population	POP_Fn	POP_Tn	POP_Ln
Efficacy	EFF_Fn	EFF_Tn	EFF_Ln
Safety	SAFE_Fn	SAFE_Tn	SAFE_Ln
Pharmacokinetic	PK_Fn	PK_Tn	PK_Ln
Pharmacodynamic and / or Biomarker	PD_Fn	PD_Tn	PD_Ln
Pharmacokinetic / Pharmacodynamic	PKPD_Fn	PKPD_Tn	PK/PD_Ln

NOTES:

• Non-Standard displays are indicated in the 'IDSL / TST ID / Example Shell' or 'Programming Notes' column as '[Non-Standard] + Reference.'

10.8.3. Deliverable [Priority]

Delivery	Description
SAC	Final Statistical Analysis Complete

10.8.4. Study Population Tables

Study Popu	Study Population Tables						
No.	Populati on	IDSL / TST ID / Example Shell	Title	Programming Notes	Deliverable [Priority]		
1.1.	Safety	ES1	Summary of Subject Disposition		SAC		
1.2.	All Screened	ES6	Summary of Reasons for Screen Failure		SAC		
1.3.	All Screened	SP1	Summary of Study Populations		SAC		
1.4.	Safety	DM1	Summary of Demographic Characteristics		SAC		
1.5.	Safety	DM5	Summary of Race and Racial Combinations		SAC		
1.6.	Safety	DM6	Summary of Race and Racial Combination Details		SAC		
1.7.	Safety	MH1	Summary of Current/Past Medical Conditions		SAC		
1.8.	Safety	CM1	Summary of Concomitant Medications		SAC		

10.8.5. PET Tables

PET: Ta	ibles				
No.	Population	IDSL / TST ID / Example Shell	Title	Programming Notes	Deliverable [Priority]
2.1.	PK	PET1	Summary of Mean SUV for Each Organ at All Time Points		SAC
2.2.	PK	PET1	Summary of Peak SUV for Each Organ at All Time Points		SAC
2.3.	PK	PET1	Summary of Max SUV for Each Organ at All Time Points		SAC
2.4.	РК	PET1	Summary of Volume of Regions of Interest for Each Organ at All Time Points		SAC
2.5.	PK	PET1	Summary of Percent Injected Dose for Each Organ at All Time Points		SAC
2.6.	PK	PET1	Summary of Activity Concentration Mean for Each Organ at All Time Points		SAC
2.7.	PK	PET1	Summary of Total Uptake values for Each Organ at All Time Points		SAC
2.8.	PK	PET1	Summary of Organ And Effective Dose		SAC

10.8.6. PET Figures

Efficacy	/: Figures				
No.	Population	IDSL / TST ID / Example Shell	Title	Programming Notes	Deliverable [Priority]
2.1.	РК	FIG1	Individual Subject Single Panel Plot : Mean SUV over Time	Y-axis: Result X-axis : Planned Time Points	SAC
2.2.	PK	FIG1	Individual Subject Single Panel Plot : Peak SUV over Time	Y-axis: Result X-axis : Planned Time Points	SAC
2.3.	PK	FIG1	Individual Subject Single Panel Plot : Max SUV over Time	Y-axis: Result X-axis : Planned Time Points	SAC
2.4.	PK	FIG2	Mean Profile (mean +/- SE) Plot : Mean SUV over Time	Y-Axis :Mean +/- SE X- Axis: Time Points	SAC
2.5.	PK	FIG2	Mean Profile (mean +/- SE) Plot : Peak SUV over Time	Y-Axis :Mean +/- SE X- Axis: Time Points	SAC
2.6.	PK	FIG2	Mean Profile (mean +/- SE) Plot : Max SUV over Time	Y-Axis :Mean +/- SE X- Axis: Time Points	SAC
2.7.	PK	FIG1	Percent Injected Dose over time	Y-Axis : Percent Injected Dose X-axis : Time Points	SAC

10.8.7. Pharmacokinetic Tables

PK : Ta	bles					
No.	Population	IDSL / TST ID / Example Shell	Title	Programming Notes	Deliverable [Priority]	
PK Con	PK Concentration					
3.1.	PK	PK01	Summary of Whole blood concentration of 89Zr-GSK3128349 Pharmacokinetic Concentration-Time Data		SAC	
3.2.	PK	PK01	Summary of Plasma Concentration of ⁸⁹ Zr-GSK3128349 Pharmacokinetic Concentration-Time Data		SAC	
3.3.	PK	PK01	Summary of Plasma Concentration of GSK3128349 Pharmacokinetic Concentration-Time Data		SAC	
3.4.	PK	PK01	Summary of Urine Concentration of ⁸⁹ Zr-GSK3128349 Pharmacokinetic Concentration-Time Data		SAC	
PK Para	ameters					
3.5.	PK	PK06	Summary of Derived Pharmacokinetic parameters for whole blood concentration of ⁸⁹ Zr-GSK3128349(non-transformed and log-transformed)		SAC	
3.6.	PK	PK06	Summary of Derived Pharmacokinetic parameters for plasma concentration of ⁸⁹ Zr-GSK3128349(non-transformed and log-transformed)		SAC	
3.7.	PK	PK06	Summary of Derived Pharmacokinetic parameters for plasma concentration of GSK3128349(non-transformed and log-transformed)		SAC	

